#### **7.4. Pause Rules**

Not applicable for this study.

## **8. STUDY ASSESSMENTS AND PROCEDURES**

Before performing any study procedures, all potential participants will sign an ICF (as detailed in [Section 10.1.3](#)). Participants will undergo study procedures at the timepoints specified in the SoA ([Table 1](#)).

A participant can also be seen for an unscheduled visit at any time during the study. An unscheduled visit may be prompted by new or ongoing AEs. The study site also has the discretion to make safety telephone calls or send text messages to remind the participant about visits or follow up with ongoing or outstanding issues.

General considerations for study assessments and procedures include the following:

- Study procedures and their timing are summarized in the SoA ([Table 1](#)). Protocol waivers or exemptions are not allowed. Adherence to the study design requirements, including those specified in the SoA, is essential and required for study conduct.
- All screening evaluations must be completed and reviewed to confirm that potential participants meet all eligibility criteria. The Investigator will maintain a screening log to record details of all participants screened and to confirm eligibility or record reasons for screening failure, as applicable.
- Immediate safety concerns should be discussed with the Sponsor immediately upon occurrence or awareness to determine if the participant should continue study vaccination or participation in the study.

The maximum amount of blood collected from each participant over the duration of the study, including any extra assessments that may be required, will not exceed blood limits specified by local regulations.

Repeat or unscheduled samples may be taken for safety reasons or for technical issues with the samples. Further details are provided in both the ICF and Laboratory Reference Manual.

### **8.1. Efficacy and/or Immunogenicity Assessments**

No efficacy and/or immunogenicity assessments are planned in this study.

### **8.2. Safety Assessments**

Planned timepoints for all safety assessments are provided in the SoA ([Table 1](#)).

Safety assessments will include monitoring and recording of the following for each participant:

- AEs leading to withdrawal from injection on Day 1 through EOS.
- MAAEs from injection on Day 1 through EOS.
- AESIs from injection on Day 1 through EOS.
- SAEs from informed consent signing through EOS.
- Vital sign measurements before and after injection.
- Physical examination findings (if performed after initial exam).

- Details of all pregnancies ([Section 10.3.2](#)) in POCBP participants will be collected after the start of study intervention and until the end of their participation in the study. All pregnancies must be followed to determine the outcome; however, pregnancy-related data received after the end of the study may not be collected in the clinical database.
- Concomitant medications and nonstudy vaccinations.

### **8.2.1. Safety Phone Calls**

A safety telephone call is a telephone call made to the participant by trained study site personnel.

The study site has the discretion to make reminder telephone calls or send text messages to inform the participant about visits or follow-up on ongoing or outstanding issues ([Section 1.3](#)).

The participant may be asked about the occurrence of SAEs, MAAEs, AESIs, AEs leading to withdrawal, concomitant medications relevant to or for the treatment of the SAEs, MAAEs, AESIs, and AEs leading to withdrawal, and any nonstudy vaccinations ([Section 8.2](#)). All safety information collected from the telephone contact must be documented in source documents as described by the participant.

As noted in [Section 8](#), an unscheduled follow-up safety telephone call may be triggered by identification of a relevant safety event.

### **8.2.2. Use of Electronic Diaries**

Participants will be asked to use an eDiary to collect information about strenuous physical exercise at the timepoints provided in [Table 2](#). If an elevated cTnI level is detected during the analysis, the activity data for that participant will be reviewed for correlation of vigorous physical activities with elevated cTnI levels.

Study site staff will review eDiary data with participants at each clinic visit after the first injection.

### **8.2.3. Physical Examinations**

- A full physical examination, including height and weight, will be performed at scheduled timepoints as indicated in the SoA ([Table 1](#)). The full examination will include assessment of skin, head, ears, eyes, nose, throat, neck, thyroid, lungs, heart, cardiovascular system, abdomen, lymph nodes, and musculoskeletal system/extremities.
- Symptom-directed physical examinations may be performed at other timepoints at the discretion of the Investigator. Any abnormalities should be documented.
- Body mass index will be calculated at the Screening/Baseline Visit only.

### **8.2.4. Vital Signs**

Vital sign measurements will include systolic and diastolic blood pressure, pulse rate, respiratory rate, and body temperature (preferred route is oral). The participant will be seated for at least

5 minutes before all measurements are taken. Vital signs will be measured at the timepoints indicated in the SoA ([Table 1](#)).

- For participants who are febrile (body temperature  $\geq 38.0^{\circ}\text{C}$  [ $100.4^{\circ}\text{F}$ ]) before injection on Day 1, the visit must be rescheduled within the relevant window period to receive the injection. Afebrile participants with minor illnesses can be administered study intervention at the discretion of the Investigator.
- Vital signs will be assessed before and approximately 15 minutes after injection on the day of injection (Day 1 and Day 29).
- When procedures overlap and are scheduled to occur at the same timepoint, the order of procedures should be vital sign measurements and then blood collection.

#### **8.2.5. Clinical Safety Laboratory Tests**

Planned timepoints for blood collections for assessing cTnI levels are provided in the SoA ([Table 1](#)); blood samples will be collected prior to administration of study injection. Elevated cTnI levels will be defined as per the threshold described in product insert of the hs-cTnI assay kit. As this is a blinded study, the results of the hs-cTnI assay will not be available until after the study is completed, and therefore will not be shared with the participant during the study.

No scheduled laboratory assessments for safety are planned. This is based on the absence of clinically significant abnormal laboratory findings in the Phase 1 and Phase 2 studies of mRNA-1273 in adults.

#### **8.2.6. Pregnancy Testing**

Planned timepoints for collection of highly sensitive urine hCG pregnancy test for POCBP are provided in the SoA ([Table 1](#)); samples will be collected before administration of study injection.

- Refer to [Section 5.1](#) (Inclusion Criteria) for pregnancy testing entry criteria.
- At any time, a pregnancy test, either via blood or point-of-care urine, can be performed, as determined necessary by the Investigator or required by local regulation, to establish the absence of pregnancy at any time during the participant's participation in the study.

### **8.3. AEs: Procedures for Recording, Evaluating, Follow-up, and Reporting**

The definitions of AEs, SAEs, SUSARs, MAAEs, and AESIs, are provided in [Section 8.3.1](#). The time period and frequency for collecting safety information is provided in [Section 8.3.2](#). The method of detecting AEs and SAEs is provided in [Section 8.3.3](#). The method of recording AEs and SAEs is described in [Section 8.3.4](#). The assessment of intensity and causality is provided in [Section 8.3.5](#). The follow-up of AEs and SAEs is described in [Section 8.3.6](#). The reporting of SAEs/AESIs is described in [Section 8.3.7](#). Regulatory reporting requirements are provided in [Section 8.3.8](#). Pregnancy reporting is provided in [Section 8.3.9](#).

The Investigator and any qualified designees are responsible for detecting, documenting, and recording events that meet the definition of an AE or SAE and remain responsible for following

up AEs that are serious, considered related to the study intervention or study procedures, or that caused the participant to discontinue the study intervention or study (see [Section 6.9.3](#)). This includes events reported by the participant (or, when appropriate, by a caregiver, surrogate, or the participant's legally authorized representative).

Medication errors, pregnancies, and uses outside of the study protocol (including misuse and abuse) are being subject to the same collection/reporting rules as AEs.

### **8.3.1. Safety Events**

AEs are defined in [Section 8.3.1.1](#). SAEs are defined in [Section 8.3.1.2](#). SUSARs are defined in [Section 8.3.1.3](#). MAAEs are defined in [Section 8.3.1.4](#). AESIs are defined in [Section 8.3.1.5](#). Solicited adverse reactions will not be collected in this study.

#### **8.3.1.1. Adverse Event**

- An AE is any untoward medical occurrence in a clinical study participant, temporally associated with the use of study intervention, whether or not considered related to the study intervention.

NOTE: An AE can therefore be any unfavorable and unintended sign (including an abnormal laboratory finding), symptom, or disease (new or exacerbated) temporally associated with the use of study intervention.

#### **Events Meeting the AE Definition**

- Any abnormal laboratory test results (hematology, clinical chemistry, or urinalysis) or other safety assessments (eg, ECG, radiological scans, vital signs measurements), including those that worsen from baseline, considered clinically significant in the medical and scientific judgment of the Investigator (ie, not related to progression of underlying disease, or more severe than expected for the participant's condition).
- Exacerbation of a chronic or intermittent preexisting condition including either an increase in frequency and/or intensity of the condition.
- New condition detected or diagnosed after study intervention administration even though it may have been present before the start of the study.
- Signs, symptoms, or the clinical sequelae of a suspected interactions with other vaccines.
- Signs, symptoms, or the clinical sequelae of a suspected overdose of either study intervention or a concomitant medication. Overdose per se will not be reported as an AE/SAE unless it is an intentional overdose taken with possible suicidal/self-harming intent. Such overdoses should be reported regardless of sequelae.
- The signs, symptoms, and/or clinical sequelae resulting from lack of efficacy will be reported as an AE or SAE if they fulfill the definition of an AE or SAE. Lack of efficacy or failure of expected pharmacological action also constitutes an AE or SAE.

### **Events not Meeting the AE Definition**

- Any abnormal laboratory findings or other abnormal safety assessments that are associated with the underlying disease, unless judged by the Investigator to be more severe than expected for the participant's condition.
- The disease/disorder being studied or expected progression, signs, or symptoms of the disease/disorder being studied, unless more severe than expected for the participant's condition.
- Medical or surgical procedure (eg, endoscopy, appendectomy): the condition that leads to the procedure is the AE.
- Situations in which an untoward medical occurrence did not occur (social and/or convenience admission to a hospital).
- Anticipated day-to-day fluctuations of preexisting disease(s) or condition(s) present or detected at the start of the study that do not worsen.

#### **8.3.1.2. Serious Adverse Event**

An SAE is defined as any untoward medical occurrence that meets one or more of the criteria listed:

**a. Results in death.**

**b. Is life-threatening.**

- The term life-threatening in the definition of serious refers to an event in which the participant was at risk of death at the time of the event. It does not refer to an event, which hypothetically might have caused death, if it were more severe.

**c. Requires inpatient hospitalization or prolongation of existing hospitalization.**

- In general, hospitalization signifies that the participant has been admitted (usually involving at least an overnight stay) at the hospital or emergency ward for observation and/or treatment that would not have been appropriate in the physician's office or outpatient setting. Complications that occur during hospitalization are AEs. If a complication prolongs hospitalization or fulfills any other serious criteria, the event is serious. When in doubt as to whether hospitalization occurred or was necessary, the AE should be considered serious.
- Hospitalization for elective treatment of a preexisting condition that did not worsen from baseline is not considered an AE.
- Results in persistent or significant disability/incapacity.

The term disability means a substantial disruption of a person's ability to conduct normal life functions.

- This definition is not intended to include experiences of relatively minor medical significance such as uncomplicated headache, nausea, vomiting, diarrhea, influenza, and accidental trauma (eg, sprained ankle) that may interfere with or prevent everyday life functions but do not constitute a substantial disruption.

**d. If exposure to a study intervention prior to conception or during pregnancy may have resulted in birth defects, congenital disorders, congenital malformations, or congenital abnormalities.**

**e. Other situations:**

- Important medical events that may not be immediately life-threatening or result in death or hospitalization but may jeopardize the participant or may require medical or surgical intervention to prevent one of the other outcomes listed in the above definition. These events should usually be considered serious.

#### **8.3.1.3. Suspected Unexpected Serious Adverse Reaction**

A SUSAR is an AE that occurs in a clinical study participant, which is assessed by the Sponsor and/or the Investigator as being unexpected, serious, and having a reasonable possibility of a causal relationship with the study intervention.

#### **8.3.1.4. MAAE**

A MAAE is an AE that leads to an unscheduled visit to a healthcare practitioner. This would include visits to a study site for unscheduled assessments not required per protocol (eg, rash assessment, abnormal laboratory follow-up) and visits to healthcare practitioners external to the study site (eg, emergency room, urgent care, primary care physician).

#### **8.3.1.5. AESI**

An AESI is an AE (serious or nonserious) of scientific and medical concern specific to the Sponsor's product or program, for which ongoing monitoring and immediate notification by the Investigator to the Sponsor are required. Such events may require further investigation to characterize and understand them.

The AESIs defined for this protocol can be found in [Section 10.5](#).

##### **8.3.1.5.1. Anaphylaxis**

All suspected cases of anaphylaxis associated with study intervention administration should be recorded as AESIs and reported as an SAE ([Section 8.3.7](#)), based on criteria for a medically important event, unless the event meets other serious criteria. As an SAE, the event should be reported to the Sponsor or designee immediately and in all circumstances within 24 hours as per [Section 8.3.7](#) (Reporting SAEs). For reporting purposes, a participant who displays signs/symptoms consistent with anaphylaxis as shown below should be reported as a potential case of anaphylaxis. This is provided as general guidance for Investigators and is based on the Brighton Collaboration case definition ([Rüggeberg et al 2007](#)).

Anaphylaxis is an acute hypersensitivity reaction with multi-organ system involvement that can present as, or rapidly progress to, a severe life-threatening reaction. It may occur following exposure to allergens from a variety of sources. Anaphylaxis is a clinical syndrome characterized by:

- Sudden onset AND
- Rapid progression of signs and symptoms AND

- Involving 2 or more organ systems, as follows:
  - Skin/mucosal: urticaria (hives), generalized erythema, angioedema, generalized pruritus with skin rash, generalized prickle sensation, red and itchy eyes.
  - Cardiovascular: measured hypotension, clinical diagnosis of uncompensated shock, loss of consciousness or decreased level of consciousness, evidence of reduced peripheral circulation.
  - Respiratory: bilateral wheeze (bronchospasm), difficulty breathing, stridor, upper airway swelling (lip, tongue, throat, uvula, or larynx), respiratory distress, persistent dry cough, hoarse voice, sensation of throat closure, sneezing, rhinorrhea.
  - Gastrointestinal: diarrhea, abdominal pain, nausea, vomiting.

#### **8.3.1.5.2. Myocarditis and/or Pericarditis**

A case of suspected, probable, or confirmed myocarditis, pericarditis, or myopericarditis should be reported as an AESI, even if it does not meet criteria per the CDC case definition. The event should also be reported as an SAE if it meets seriousness criteria ([Section 8.3.1.2](#)).

The Investigator's medical judgment must be applied when assessing participants reporting symptoms concerning myocarditis and/or pericarditis contained within the CDC case definition.

Diagnostic evaluation (eg, ECG/EKG) and laboratory testing (eg, troponin) should be obtained promptly if considered clinically indicated in any participant with concerning signs/symptoms. Diagnostic imaging (eg, cMRI, echocardiogram) should be obtained in those with positive diagnostic or laboratory test results or clinically significant symptoms for myocarditis/ pericarditis without other identifiable causes. The participant should be referred to a cardiologist. Additional testing and evaluation may be indicated.

The Investigator will submit any updated myocarditis, pericarditis, or myopericarditis case data to the Sponsor within 24 hours of it being available. Cases of myocarditis and pericarditis will be followed until resolution of symptoms and abnormal test findings. Participants with events of myocarditis and/or pericarditis will continue to be followed in the study for safety as per the protocol.

An independent CEAC will review all suspected cases of myocarditis, pericarditis, and myopericarditis, which are reported in ongoing interventional clinical studies per the CEAC charter, to determine if they meet CDC cases classification as "probable" or "confirmed" events. The CDC Working Case Definitions are provided in [Section 10.5](#) as guidance, and the CEAC is described in [Section 10.1.6](#).

#### **8.3.2. Time Period and Frequency for Collecting of Safety Information**

All MAAEs, AESIs, and AEs leading to withdrawal will be collected after injection on Day 1 until EOS at the timepoints specified in the SoA ([Table 1](#)). All SAEs will be collected from signing of informed consent until EOS at the timepoints specified in the SoA ([Table 1](#)). All SAEs will be recorded and reported to the Sponsor or designee immediately and under no circumstance should this exceed 24 hours, as indicated in [Section 8.3.7](#). The Investigator will submit any updated SAE data to the Sponsor within 24 hours of it being available.

Investigators are not obligated to actively seek information on AEs or SAEs after conclusion of the study participation. However, if the Investigator learns of any SAE, including a death, at any time after a participant has been discharged from the study, and the Investigator considers the event to be reasonably related to the study intervention or study participation, the Investigator must promptly notify the Sponsor.

Medical occurrences that begin before the start of study intervention but after obtaining informed consent will be recorded as medical history/current medical conditions, not as AEs; however, if the condition worsens at any time after study intervention administration, it will be recorded and reported as an AE if it meets reporting criteria.

### **8.3.3. Method of Detecting AEs and SAEs**

Care will be taken not to introduce bias when detecting AEs and/or SAEs. Open-ended and nonleading verbal questioning of the participant is the preferred method to inquire about AE occurrences.

### **8.3.4. AE and SAE Recording**

- When an AE/SAE occurs, it is the responsibility of the Investigator to review all documentation (eg, hospital progress notes, laboratory reports, and diagnostics reports) related to the event.
- The Investigator will then record all relevant AE/SAE information.
- It is **not** acceptable for the Investigator to send photocopies of the participant's medical records to the Sponsor in lieu of completion of the required form.
- There may be instances when copies of medical records for certain cases are requested by the Sponsor. In this case, all participant identifiers, with the exception of the participant number, will be redacted on the copies of the medical records before submission to the Sponsor.
- The Investigator will attempt to establish a diagnosis of the event based on signs, symptoms, and/or other clinical information. Whenever possible, the diagnosis (not the individual signs/symptoms) will be documented as the AE/SAE.

### **8.3.5. Assessment of Intensity and Causality**

The Investigator will make an assessment of intensity for each AE and SAE reported during the study and assign it to one of the following categories:

- **Mild:**  
A type of AE that is usually transient and may require only minimal treatment or therapeutic intervention. The event does not generally interfere with usual activities of daily living.
- **Moderate:**  
A type of AE that is usually alleviated with additional specific therapeutic intervention. The event interferes with usual activities of daily living, causing discomfort but poses no significant or permanent risk of harm to the participant.

- **Severe:**

A type of AE that interrupts usual activities of daily living, or significantly affects clinical status, or may require intensive therapeutic intervention.

### Assessment of Causality

- The Investigator is obligated to assess the relationship between study intervention and each occurrence of each AE/SAE. The Investigator will use clinical judgment to determine the relationship.
  - **Not related:** There is not a reasonable possibility of a relationship to the study intervention. Participant did not receive the study intervention OR temporal sequence of the AE onset relative to administration of the study intervention is not reasonable OR the AE is more likely explained by another cause than the study intervention.
  - **Related:** There is a reasonable possibility of a relationship to the study intervention. There is evidence of exposure to the study intervention. The temporal sequence of the AE onset relative to the administration of the study intervention is reasonable. The AE is more likely explained by the study intervention than by another cause.
- For causality assessment, the Investigator will also consult the IB and/or product information, for marketed products.
- The Investigator must review and provide an assessment of causality for each AE/SAE and document this in the medical notes. There may be situations in which an SAE has occurred and the Investigator has minimal information to include in the initial report to the Sponsor. However, it is very important that the Investigator always make an assessment of causality for every event before the initial transmission of the SAE data to the Sponsor.
- The Investigator may change their opinion of causality in light of follow-up information and send an SAE follow-up report with the updated causality assessment.
- The causality assessment is one of the criteria used when determining regulatory reporting requirements.

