#### **6.4.1.2. AEs by System Organ Class and Preferred Term**

The following summary tables of AEs will be provided by SOC and PT using frequency counts and percentages (i.e., number and percentage of participants with an event):

- All SAEs and all SAEs that are treatment-related
- All MAAEs and all MAAEs that are treatment-related
- All AESIs and all AESIs that are treatment-related
- All unsolicited AEs leading to discontinuation from study vaccine and all unsolicited AEs leading to discontinuation from study vaccine that are treatment-related
- All unsolicited AEs leading to discontinuation from participation in the study and all unsolicited AEs leading to discontinuation from participation in the study that are treatment-related

- All unsolicited AEs, defined as SAEs, MAAEs, AESIs, and AEs leading to withdrawal IP and study participation, and all unsolicited AEs that are treatment-related

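### Protocol 8.3.5 defines relatedness by two conflicting tests, and the stricter one departs from the reasonable-possibility standard used for SUSARs

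*Protocol*

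**What the plan says.** Protocol 8.3.5 (Assessment of Causality) gives the investigator two categories for every AE and SAE.

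- **Related** begins "There is a reasonable possibility of a relationship to the study intervention". Sentences on exposure and timing follow, and then "The AE is more likely explained by the study intervention than by another cause". No AND or OR joins these sentences.
- **Not related** begins "There is not a reasonable possibility of a relationship to the study intervention". It then lists alternatives, the last being "OR the AE is more likely explained by another cause than the study intervention".

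The same section says "The Investigator will use clinical judgment to determine the relationship". It requires a causality assessment for every event before the first SAE transmission, and names causality as one of the criteria for regulatory reporting.

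Protocol 8.3.1.3 defines a SUSAR as an event assessed by the sponsor, the investigator or both as "being unexpected, serious, and having a reasonable possibility of a causal relationship with the study intervention". It contains no comparison with other causes.

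The SAP gives no causality definition of its own. It relies on the investigator's category in the treatment-related tables of 6.4.1.1 to 6.4.1.3, for example "All SAEs and all SAEs that are treatment-related". In 6.4.1 it also uses relatedness to choose which event and severity to show when a participant has several.

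**The concern.** A reasonable possibility and a greater likelihood than any alternative are different thresholds, and 8.3.5 uses both for the same decision. They part company for events with a plausible competing cause. Such events are foreseeable here: the protocol notes that myocarditis can follow SARS-CoV-2 infection (2.1), and it asks for AESI reporting even when the event occurs during or after COVID infection (Appendix 2).

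At stake is what a treatment-related count means. If one site works from the lead sentences and another from the sub-criteria, the same event can be classified differently, and a reader of the tables cannot tell which standard was applied.

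**Working it through.** The plan attaches no figure to causality, so there is none to reproduce. The check sets the definitions side by side.

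**1. The tests.**

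| Place | Test | How it operates |
|---|---|---|
| 8.3.5, lead sentences | Reasonable possibility, yes or no | Complementary; every event has a category |
| 8.3.5, Related, last sentence | Intervention likelier than another cause | No connective; reads most naturally as a further condition |
| 8.3.5, Not related, last clause | Another cause likelier | Joined by OR; sufficient alone |
| 8.3.1.3, SUSAR | Reasonable possibility | Sponsor's or investigator's assessment is enough |

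**2. Enumerate the sub-criteria.** Take exposure (yes/no), reasonable timing (yes/no) and relative likelihood (intervention, tie, other cause): 2 × 2 × 3 = 12 combinations. Read the Related sentences as cumulative and the Not related clauses as alternatives. Then 1 combination is Related, 10 are Not related and 1 has no category. These are counts of logical cases, not of expected events.

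**3. Compare with the reasonable-possibility standard.** The difference lies among exposed, well-timed events for which a reasonable possibility exists:

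| Likelier explanation | Lead sentences of 8.3.5, and 8.3.1.3 | Sub-criteria of 8.3.5 |
|---|---|---|
| Study intervention | Meets the standard | Related |
| Equally likely | Meets the standard | Neither category |
| Another cause | Meets the standard | Not related |

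In the third row a single event satisfies the lead sentence of Related, the OR clause of Not related, and the causal part of the SUSAR definition.

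**4. Direction.** Where the relative-likelihood test changes a category that reasonable possibility would give, it moves the event from Related to Not related. Any effect on the count of related events is therefore downward.

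**5. Event shown for a participant.** Under SAP 6.4.1, a participant with both related and unrelated events is shown by the most severe related one. Suppose, as an illustration, a severe unrelated event and a mild event that is possible but less likely vaccine-related. Under reasonable possibility the mild event is related and is the one shown. Under the relative test both are unrelated and the severe one is shown. The effect on displayed severity can thus go either way.

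**6. Notification.** During participation, all SAEs go to the sponsor within 24 hours whatever their causality (8.3.2). After discharge, 8.3.2 requires notification of an SAE only if the investigator considers it reasonably related to the intervention or to participation; 8.3.9 applies a similar condition to poststudy pregnancy-related SAEs. If investigators read that condition through the relative test, a possible but less likely event might not be sent.

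**The case against.** The strongest reply is that little rests on the investigator's category. The secondary safety endpoint (Protocol Table 3, SAP 3.2) carries no relatedness condition, and every treatment-related table accompanies an all-event table, so no event is lost. Investigators are blinded, so the same rule applies in vaccine and placebo periods. Suspected myocarditis or pericarditis is reported as an AESI even when it falls short of the CDC definition (8.3.1.5.2), all suspected cases go to an independent adjudication committee, and SAP 6.4.1.4 summarises these events without a relatedness filter. All of this stands, and it limits the point to the treatment-related displays and post-study notification.

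A reader might infer that SUSARs are under-counted. The documents do not support that for the study period. Section 8.3.1.3 keeps the reasonable-possibility standard and lets the sponsor's assessment alone qualify an event, and the sponsor receives every SAE. A Not related mark from the investigator does not by itself remove a SUSAR.

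A reader might also infer that ties have no category at all. That is true of the sub-criteria only; the lead sentences would place a tie with a reasonable possibility under Related. The missing connective and the reliance on clinical judgment do leave room for that reading. They do not override a written clause that makes a likelier other cause sufficient for Not related, and the availability of two readings is itself the difficulty.

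**Conclusion.** The point holds as an inconsistency of definition. Section 8.3.5 contradicts its own lead sentences and departs from 8.3.1.3. Read literally, it files possible but less likely events as Not related and leaves ties outside both sets of sub-criteria. Treatment-related counts may consequently be lower than the stated standard would give, or inconsistent between sites, and the event and severity shown under SAP 6.4.1 may change. Post-study notification is exposed only if investigators carry the same test into the reasonably-related condition.

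This rests on reading the Related sentences as cumulative and the Not related clauses as alternatives. It shows what the wording permits, not that under-counting has occurred. No size can be given: the documents contain neither AE rates nor any distribution of causal likelihood, and a percentage would only restate whatever distribution was assumed. The primary cTnI endpoint, the sample size, the all-event safety tables, AESI reporting and the myocarditis/pericarditis summaries are unaffected.

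**What to change.** Use one standard in Protocol 8.3.5, the one already in 8.3.1.3: Related if there is a reasonable possibility of a causal relationship, Not related if there is none. Delete the Related sentence "The AE is more likely explained by the study intervention than by another cause" and the Not related alternative "the AE is more likely explained by another cause than the study intervention", or keep other causes only as a factor the investigator weighs in judging whether a reasonable possibility exists. Each event then has exactly one category, ties and possible-but-less-likely events included, and the SAP's treatment-related tables use the same causal standard as the SUSAR definition.

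The cost is a protocol wording change and matching eCRF completion guidance. No change to the analysis methods is needed. Treatment-related counts may be somewhat higher than under the current wording.
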